- a description of whether there are any local changes to the protocol s procedures, and if so, what those changes are (i.e. different, omitted, or additional procedures)
- any necessary clarifications of the protocol s content (i.e. what local standard of care or routine practice
- A description of all research measures/tests/interventions that will be used (if applicable)
- A detailed description or list of all secondary data elements and/or secondary specimens that will be obtained and how they will be used (if applicable)

See the help text for additional guidance.

This study will be a prospective study of patients with compensated cirrhosis This study will be divided into screening and post-ramelteon visits

For this study, we will recruit patients with cirrhosis from the hepatology clinic.

Inclusion criteria:

a. Child class A cirrhosis proven by biopsy, radiology or endoscopic evidence of varices b. Able to give informed consent

Exclusion criteria

- a. Diagnosed sleep apnea b. Use of sleep aids
- c. Moderate to severe depression
- d. Unable to give informed consent
- e. Night shift workers
- f. Inter-continental travel within the last 4 weeks
- g. Renal insufficiency on dialysis h. Current alcohol or illicit drug use
- i. Diabetes Mellitus using insulin therapy
- j. Use of chronic hypnotic medications more than once per week or more than 5-6 times per month K. Positive Berlin Questionnaire
- L. Becks Inventory Questionnaire Greater than or equal to 20 without the suicide question. m. Patient unwilling to start therapy
- n. Allergic reactions to ramelteon in the past

Screening: All subjects will come for an initial screening visit to the CRSU at which point the following procedures will be performed

- a Vitals including BMI
- b. Skinfold thickness and waist-hip ratio
- c. Beck Depression Inventory (BDI)
- d. Sickness impact profile for overall HRQOL
- e. Questionnaires regarding sleep
- f Berlin questionnaire
- g. STOP Bang questionnaire
- h. Epworth sleepiness scale (ESS) and i. Pittsburgh sleep quality index (PQSI)

Cirrhotic patients with a Positive Berlin questionnaire will be excluded because these are highly suggestive of sleep disturbances and OSA11, 12. We will also exclude patients who have evidence of moderate to severe depression on Beck Depression Inventory (score ≥20) without the suicide question. They will be paid \$25 for their time.

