All enrolled study participants will perform 5 paper-pencil and two computerized tests of intelligence which will last approximately 35 minutes total. RAMELTEON THERAPY :

The subjects' study chart, current medications, medical history and pregnancy testing will be assessed by [name] and [name] who will then decide if this patient would benefit from ramelteon. The criteria used will be insomnia along with the absence of OSA by the questionnaires. Ramelteon is an FDA-

approved selective melatonin receptor 1 and 2 analog indicated for use in insomnia. The dose used will be 8 mg, the lowest possible dose. If the sleep specialists believe that a particular cirrhotic patient is a candidate for this therapy, they will be clinically prescribed ramelteon after a detailed face to face visit explaining the risks and benefits. Ramelteon is not indicated in patients with severe hepatic impairment (defined as Child Class C), therefore, these patients will not be included in the study.

if the patient agrees to take the medicine, it will be dispensed through the investigational pharmacy, where it will be stored for this study. Patients will be asked to complete a medication and sleep diary for the duration of the drug therapy which will be a maximum of 15 days. Within 15 days of drug initiation, the patients will be asked to complete the sleep questionnaires again and cognitive testing similar to that described in visit 1. They will be paid \$75 for this part of the study.

Date: Tuesday, March 2, 2021 3:54:08 PM

ID: HM13968

Print	Close
-------	-------

View: SF - Bio-Med Project Details

HM13968 - [name] Study of Sleep in Cirrhosis

Bio-Med Project Details

1. 1	Select	all	that	apply	to	this	study	
------	--------	-----	------	-------	----	------	-------	--

~	Drug(s) / Biologics / Supplement(s) / Other Compounds (investigational products or products whose administration is dictated by the study protocol and not per the physician's clinical judgment)
	Bio-Hazards, Other Toxins, Recombinant DNA/Gene Transfer
	Safety and/or effectiveness evaluation of Bio-Medical Device(s), including in-vitro diagnostic devices/assays mobile medical apps, and HUDs used in clinical investigations
	Radiation Exposure and/or Scans involving radiation (eg: PET, MRA, CT, DXA, nuclear medicine, etc)
	Stem Cells
~	Medical or Surgical Procedures (eg physical exam, clinical procedures, scans, etc)
~	Protected Health Information (PHI)
_	None of the Above

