ID: HM13968

Print Close

View: SF - Potential Subject Identification and Recruitment

HM13968 - [name] Study of Sleep in Cirrhosis

Potential Subject Identification and Recruitment

 1. * Choose all recruitment methods that may be used

 □
 E-mail invitations

 □
 Phone Solicitation scripts (i.e. cold calls or random-digit-dialing)

 □
 Flyers, Mailed Letters or Newspaper/TV/Radio Ads

 □
 Website text

 □
 Direct Contact

 □
 Psychology Research

 □
 VCU TelegRAM announcement

 □
 Word of Mouth

 □
 Participant Pool (SONA)

 □
 Other recruitment material

 2. If Other, please describe
 3. * Select the methods used to obtain names and contact information for potential subjects

~	Pre-Existing Relationship with Participants
~	Selected from Pre-Existing VCU Records
	Selected from Pre-Existing Non-VCU Records
	Selected from Publicly Available Records
~	Referred by Health Care Provider or Other Health Professional
	Recruited from Database or Registry
	Identified through Community Based Organization (Schools, Church Groups, etc.)
	Self Referred (Flyer/Ad)
	Other

4. If Other, please describe

5.* Provide a description of

- 1. How potential participants or secondary data/specimens of interest will be identified and
- 2. All procedures that will be followed to carry out recruitment and screening activities.

Include details (as applicable) about

- How secondary data/specimens that meet the study's eligibility criteria will be identified (i.e. what database(s) will be queried and the search terms that will be used)
- How potential participants will be identified and their contact information obtained
- The timing and frequency of recruitment activities
- Where and how recruitment procedures will be completed
- Who will recruit or respond to potential participants
- What and how written or verbal recruitment materials and reminders (if any) will be used
- What screening activities will occur and how these procedures will be performed

See the help text for additional guidance.

Patients will be included from the clinic All interviews will be carried out in separate rooms and only the amount of information directly needed for the study will be sought from the subjects. Subjects will be told that if there is an indication on the BDI that they are considering suicide, then they will be sent to the Emergency room; otherwise privacy and confidentiality will be maintained at all times.

6. Describe any special recruitment procedures for vulnerable populations

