type (e.g., gift card, cash, check, merchandise, drawing, extra class credit)
how it will be disbursed

Screening visit failure: \$25
Screening and initiation of rametteon visit: \$25
Post-rametteon visit: \$75

For patients : total payment for treatment visits and post-treatment sleep visit:is \$100.

 If compensation will be pro-rated, explain the payment schedule For patients : total for treatment visits and post-treatment sleep visit: \$100 will only be paid after return of the Fitbit as a lumpsum

If patients lose their Fitbit device or do not return with it, then the device itself will be considered their payment.

Date: Tuesday, March 2, 2021 4:00:12 PM

ID: HM13968

View: SF - Risks, Discomforts, Potential Harms and Benefits

Print

HM13968 - [name] Study of Sleep in Cirrhosis

Close

Risks, Discomforts, Potential Harms and Benefits

* Describe the risks of each research procedure to participants or others. For each identified risk, provide an
assessment of the anticipated seriousness and likelihood of the risk. Some examples of possible risks include
but are not limited to

- Physical risks (e.g. bodily harms or discomforts, side effects, etc.)
- Psychological risks (e.g. emotional, mental, or spiritual harms or discomforts, changes to thoughts, beliefs, or behaviors, etc.)
- Research data risks (e.g. loss of confidentiality and privacy)
- Social or legal risks (e.g. impacts on relationships or reputation, legal or criminal justice actions for self or others, etc.)
- Financial risks (e.g. impacts on income, employability, or insurability, loss of services, etc.)
- Other risks (e.g. unforeseeable risks of experimental procedures, risks related to particular study
 designs (randomization, washout, placebo, withholding care/services, deception), etc.)

See the help text for additional guidance.

Physical risks:

a. ramelteon side effects: these include excessive sleepiness, potential to sleep drive, worsening depression, and minor risk of allergic reactions; however these risks are inherent to any insomnia treatment and these will be explained in detail to the patients before they are initiated on this with the face to face visit.

Psychological risks: minor risk of anxiety after completion of cognitive tests: to alleviate this, all subjects will be informed that these are purely collected for research. Uncovering of risk of suicide through BDI will be dealt with by sending patients to the emergency room. Socio-leaal risks: none

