2. * Describe how the risks / harms will be minimized

a. A detailed discussion regarding the appropriate medication for these patients was conducted with the Sleep Department physicians and ramelteon was considered to be appropriate for use in these patients.
 b. Patients who are appropriate candidates for ramelteon based on their sleep studies will be counseled in detail regarding the adverse events and only after that will be initiated on the medication. We will also exclude those patients with moderate or severe depression from this study. They will also be given the number for the CRSU to call if there are any issues with the medications. These medications will be prescribed in close concert with the sleep physicians who are also part of this study after careful consideration of the risks and benefits.
 c. Psychological risks will be minimized by reiterating that the patients are only doing this for research and checking the BDI data and implementing plans to send patients who check suicide risk to the emergency room as needed.

- 3. If the disclosure of any of the information obtained during the study would place the individual at risk for harm (legal, reputation, emotional etc.) and the information will be recorded so that the individual could be identified, explain the protections that will be put in place to decrease the risk of disclosure
- 4. * The Code of Virginia requires that most medical personnel and all employees of institutions of higher education report suspected child/elder abuse or neglect. Is it likely investigators could discover information that would require mandatory reporting by the investigators or staff

O Yes

🔵 No

- 5. * Is it likely investigators could discover a participant's previously unknown condition (eg disease, suicidal thoughts, wrong paternity) or if a participant is engaging in illegal activities
 - O Yes

No No

- 6. If yes, explain how and when such a discovery will be handled
- 7. * Will the study's research procedures possibly identify pertinent or incidental findings that may be of importance to subjects' health?
 - O Yes

No 🔵

- * Describe any potential risks or harms to a community or a specific population based on study findings none

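### Worsening depression is a named ramelteon risk, but the visible schedule has no depression, mood or suicide-item check after the drug is started

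*Combined protocol and SAP*

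**What the plan says.** The Risks section (item 1) lists among the ramelteon side effects "worsening depression, and minor risk of allergic reactions".

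The Research Description (item 4) divides the study into a screening visit and a post-ramelteon visit. The BDI is item c of the screening procedures. The sleep questionnaires are a separate entry, item e. A BDI score of 20 or more, counted without the suicide question, excludes the patient.

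Treated patients keep a medication and sleep diary for at most 15 days. Within 15 days of starting the drug, "the patients will be asked to complete the sleep questionnaires again and cognitive testing similar to that described in visit 1".

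Suicide risk is addressed in three places:
- Potential Subject Identification and Recruitment, item 5: "if there is an indication on the BDI that they are considering suicide, then they will be sent to the Emergency room".
- Risks, item 1: "Uncovering of risk of suicide through BDI will be dealt with by sending patients to the emergency room".
- Risks, item 2c: "checking the BDI data and implementing plans to send patients who check suicide risk to the emergency room as needed".

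Two further safeguards appear in Risks, item 2b: "We will also exclude those patients with moderate or severe depression from this study" and "They will also be given the number for the CRSU to call if there are any issues with the medications". Item 11 of the same section refers to trained psychology, hepatology and sleep staff who stay in touch with the clinical research unit (CRSU).

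**The concern.** The protocol names a psychiatric harm of the drug, has a questionnaire that would help detect it, and brings treated patients back for a visit. Yet the visible schedule does not use that questionnaire at that visit.

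The emergency-room rule is triggered by a BDI response. If the only scheduled BDI comes before the first dose, the rule protects patients who already have suicidal thoughts at screening. It has no scheduled trigger for patients who develop them on treatment.

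What is at stake is patient safety, together with a basic descriptive record of a named harm. Mood is not a study aim, and the McNemar analysis of slow-wave sleep does not depend on it.

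**Working it through.** The plan states no figure on this point, so there is none to reproduce. The check is a reading of every visible statement about the BDI, sorted by when the assessment would take place.

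| Where | What it concerns | Timing |
|---|---|---|
| Research Description, item 4, exclusion L | Score of 20 or more | Screening |
| Research Description, item 4, screening item c | BDI administered | Screening |
| Research Description, item 4, text after the screening list | Exclusion for moderate to severe depression | Screening |
| Study Population, item 5, exclusion l | Score of 20 or more | Screening |
| Recruitment, item 5 | Emergency-room rule | Screening (answers a form item on recruitment and screening) |
| Risks, item 1 | Emergency-room rule | Not stated |
| Risks, item 2c | Checking BDI data | Not stated |

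Count: 5 screening + 2 untimed + 0 post-drug = 7.

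**Could the post-drug sentence include the BDI?** It names two things: the sleep questionnaires and cognitive testing. The screening list separates the BDI (item c) from the questionnaires regarding sleep (item e). The comparison with visit 1 most naturally qualifies the cognitive testing. Neither phrase brings in the BDI.

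**Could another safeguard fill the gap?**
- The entry exclusion acts before the drug. It admits scores up to 19, leaves the suicide question out of the score, and cannot detect later change.
- The diary is described as covering medication and sleep. No mood item is stated.
- The telephone number depends on the patient recognising low mood as a drug problem and calling.
- The staff provision in item 11 concerns responding to adverse events. It does not say that anyone will ask about mood.
- The only individual withdrawal criterion is a diagnosis of sleep apnea (Risks, item 9), and the pre-specified safety stopping criteria are given as none (item 10).

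**Scheduled BDI per treated patient in the visible text:** 1 before drug and 0 after, over at most 15 days of exposure.

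**Burden of adding one:** 1 form × at most 50 enrolled patients (Study Population, item 3) = at most 50 forms. The number who will actually be treated is not stated.

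**The case against.** The strongest reply is that this is an argument from silence in an incomplete text. The post-drug paragraph also omits the Fitbit, which appears under Compensation, so it is not a full list of procedures. The consent form is not available, and the text breaks off at the item on a monitoring board or plan (Risks, item 15) with no legible selection. A mood check could be specified in either place. This stands. It limits the claim to what is visible, and a cross-reference would settle the matter if the check exists.

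A second reply is that some statements are open on timing. The recruitment sentence gives no visit, so it could be moved to the untimed group, giving 4 screening, 3 untimed and 0 post-drug. Checking the BDI data is mentioned beside reassurance about research testing, which takes place at both visits. The recruitment sentence does answer a form item on recruitment and screening, so its classification is fair. Either way, the post-drug count is zero, and an untimed statement does not schedule a form.

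A third reply points to counselling before the drug, face-to-face explanation of risks, and prescribing together with sleep physicians. These are real safeguards, but none is an assessment of mood on treatment.

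Finally, one BDI at the last visit comes near or at the end of exposure and misses anyone who does not return. That is correct and limits the benefit. It would still detect worsening in patients who do return, at a point where the existing referral procedure can be used.

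**Conclusion.** The concern holds. As the visible protocol is written, no one is required to ask about depression or suicidal thoughts after ramelteon is started, although worsening depression is a named risk and the BDI is already in use. All seven BDI statements either belong to screening or carry no timing.

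The conclusion assumes that the unseen consent form and any monitoring plan do not schedule such a check. For that reason confidence is medium.

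The likely benefit is modest. Exposure is at most 15 days at 8 mg, which the protocol calls the lowest possible dose. The drug is used as approved, and patients with a BDI of 20 or more are excluded. The documents give no rate of mood worsening, so the expected number of cases cannot be stated. The primary analysis is unaffected. This is an inexpensive safety improvement that should be made, not a flaw that threatens the study's conclusions.

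**What to change.** Add to the description of the post-ramelteon visit in the Research Description, item 4:

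> The BDI used at screening, including the suicide item, is repeated at the post-ramelteon visit and reviewed before the participant leaves. The existing emergency-room procedure applies. Change from screening is reported descriptively, with no causal claim because there is no control group.

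If the consent form or a monitoring plan already schedules this check, a cross-reference at that point is enough.

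The cost is three sentences and one short questionnaire per treated patient. It needs no new visit and no new staff, and the McNemar test is unchanged.

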View	FitBit Training 2	Help article_What should I know about sleep tracking_ pdf	0.01	011012010	[name]	Other	Yes
View	FITbit Training	Help article_ How do I track my sleep_ pdf	0.01		[name]	Other	Yes

Date: Tuesday, March 2, 2021 3:58:08 PM ID: HM13968

Print	Close
-------	-------

View: SF - Types of Sites

HM13968 - [name] Study of Sleep in Cirrhosis

Types of Sites

- 1.* Select which of the following accurately describes this study
- Not Multi-site Study
 Multi-site Study [multiple sites implementing the same protocol] VCU Lead
 Multi-site Study [multiple sites implementing the same protocol] Non-VCU Lead

2.* Select all sites where study interventions or interactions will occur and/or identifiable data will be held

	~	VCU Site		
	Non-VCU Site (VCU Investigators are conducting/overseeing the conduct of the study)			
		Non-VCU Site under the oversight of a Non-VCU PI		
~				

3. * Is there a community partner in this research study

● No

Date: Tuesday, March 2, 2021 3:58:44 PM

ID: HM13968

Print	Close

View: SF - Study Population

HM13968 - [name] Study of Sleep in Cirrhosis

Study Population

1.* Provide the total number of individuals at VCU, and at other sites under the VCU IRB, that

- 1. May participate in any study interaction or intervention (including screening, consenting, and study activities) AND/OR
- 2. You may obtain any data/specimens about (regardless of identifiability)

See the help text for additional guidance.

50

- 2. If this is a multi-Center Project, what is the total anticipated number of subjects across all sites
- 3. * Provide justification for the sample size

For the study of the impact of Ramelteon on SWS in cirrhotic patients, we are planning a pre-post study on the dichotomous outcome of SWS yes/no. If we assume the the success-failure proportion (cirrhotics who experienced SWS no longer experience SWS after treatment) is 1E-1 and the failure-success proportion (cirrhotics who did not experienced SWS experience SWS after treatment) is 0.50, then a sample size 14 is required to achieve a power of at least 80%. A sample size of 20 under the same assumption yields a power of 97%. We will use a McNemar Exact Conditional Test for this analysis. To account for dropouts and those who do not wish to participate in the treatment part of the study, we will enroll 50 cirrhotic patients.

4. * List the study inclusion criteria

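### The stated power (at least 80% with 14 patients, 97% with 20) does not follow from the stated inputs, which give 37% and 57% two-sided or 49% and 70% one-sided at 5%

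*Combined protocol and SAP*

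**What the plan says.** The only power statement in the combined protocol and SAP is in Study Population, item 3. It plans a pre-post comparison of slow-wave sleep (SWS) as a yes/no outcome in treated patients.

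- **Loss of SWS after treatment (success-failure):** "cirrhotics who experienced SWS no longer experience SWS after treatment) is 1E-1".
- **Gain of SWS after treatment (failure-success):** "cirrhotics who did not experienced SWS experience SWS after treatment) is 0.50".
- **Test:** "We will use a McNemar Exact Conditional Test for this analysis".
- **Power:** "a sample size 14 is required to achieve a power of at least 80" percent, and "A sample size of 20 under the same assumption yields a power of 97" percent.
- **Enrolment:** "we will enroll 50 cirrhotic patients", to allow for dropouts and for patients who decline treatment. No rate is given for either.

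Neither alpha nor sidedness is stated. Item 1 of the same section gives 50 as the number of people who "May participate in any study interaction or intervention (including screening, consenting, and study activities").

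**The concern.** Under the exact McNemar test only discordant pairs carry information. With proportions of 0.10 and 0.50, 60% of pairs are expected to be discordant: about 8 of 14 (14 × 0.60 = 8.4) and 12 of 20. With 8 discordant pairs a two-sided 5% exact test rejects only if all 8 go the same way, yet the assumptions expect one in six (0.10/0.60) to go the wrong way. Power of 80% with 14 patients is not plausible on those terms.

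If the investigators believe 0.10 and 0.50, a study that ends with 20 evaluable patients has a 43% chance (two-sided 5%; 30% one-sided) of missing the effect it was sized for, against the 3% implied by the text. If they had a smaller loss proportion in mind, the printed assumption is wrong. In either case a reader cannot reproduce the justification from its own inputs.

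**Working it through.** **Inputs** (Study Population, item 3): p10 = 0.10, p01 = 0.50, exact conditional McNemar test, n = 14 and n = 20. Alpha is not in the document. I assume 5%, show both one-sided and two-sided results, and then relax it.

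**Method.** The number of discordant pairs is D ~ Binomial(n, p10 + p01) = Binomial(n, 0.60). Given D, the number in the favourable direction is X ~ Binomial(D, p01/(p10 + p01)) = Binomial(D, 0.8333). The test rejects when the exact Binomial(D, 0.5) p-value is at most alpha. Power is the sum over D of P(D) × P(reject | D).

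**Attempt to reproduce the plan's first figure** (n = 14, two-sided 5%). With D of 5 or fewer the test cannot reject.

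| D | Reject if X is at least | P(D) | P(reject given D) | Product |
|---|---|---|---|---|
| 6 | 6 | 0.0918 | 0.3349 | 0.0308 |
| 7 | 7 | 0.1574 | 0.2791 | 0.0439 |
| 8 | 8 | 0.2066 | 0.2326 | 0.0480 |
| 9 | 8 | 0.2066 | 0.5427 | 0.1121 |
| 10 | 9 | 0.1549 | 0.4845 | 0.0751 |
| 11 | 10 | 0.0845 | 0.4307 | 0.0364 |
| 12 | 10 | 0.0317 | 0.6774 | 0.0215 |
| 13 | 11 | 0.0073 | 0.6281 | 0.0046 |
| 14 | 12 | 0.0008 | 0.5795 | 0.0005 |

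The products sum to 0.373 (rejections in the wrong direction add a negligible amount). The plan says at least 0.80.

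**Same calculation under other alphas, p10 = 0.10:**

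| Test | n = 14 | n = 20 |
|---|---|---|
| Plan's statement | at least 80% | 97% |
| Exact, two-sided 5% | 37.3% | 57.3% |
| Exact, one-sided 5% | 49.3% | 70.3% |
| Exact, one-sided 10% | 67.0% | 82.6% |
| Exact, one-sided 20% | 82.2% | 92.5% |

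A simulation with 200,000 draws agrees: 37.2% and 57.4% two-sided, 49.1% and 70.5% one-sided.

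**Other readings with the printed inputs, at 5%:**

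- Mid-p: 49% and 67% two-sided, 61% and 79% one-sided.
- Uncorrected chi-square: 50% and 67% two-sided, 67% and 81% one-sided.
- n taken as discordant pairs: 58% and 90% two-sided, 81% and 90% one-sided.
- Proportions taken as conditional on baseline SWS, with the 80% lacking SWS in the pilot data quoted in Research Description, item 3 (p01 = 0.80 × 0.50 = 0.40, p10 = 0.20 × 0.10 = 0.02): 43% and 75% two-sided, 61% and 85% one-sided.

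None gives both printed figures.

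**What p10 would fit?** Keeping p01 = 0.50 and the exact test:

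| p10 and test | n = 14 | n = 20 |
|---|---|---|
| 0.015, one-sided 5% | 83.5% | 96.5% |
| 0.011, one-sided 5% | 85.5% | 97.4% |
| about 0, two-sided 5% | 78.8% | 97.9% |

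At 0.015 one-sided, 13 patients give 78.8%, so 14 is the minimum for 80%. At 0.011, 13 patients already give 80.9%. In the two-sided case 14 falls just short, and 15 are needed (84.9%).

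**Pairs needed if 0.10 and 0.50 stand.** Two-sided 5%: 29 pairs give 79.2% and 30 give 80.9%. One-sided 5%: 24 give 79.9% and 25 give 81.8%.

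**Power by evaluable yield from the 50.** The document gives no yield, so this range is an assumption (two-sided 5%): 20 pairs 57%, 25 pairs 71%, 30 pairs 81%, 40 pairs 91%, 50 pairs 96.5%.

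**The case against.** The best defence is that one input is damaged and the power calculation was right. Writing 0.10 as 1E-1 next to a plain 0.50 is odd, and a character could have been lost in typing or in reading the PDF. A loss proportion of 0.015 at one-sided 5% reproduces both 14 as the minimum and 97% at 20. This possibility stands. It does not rescue the passage: a near-zero proportion at two-sided 5% also comes within 2 points of both figures, so the reader cannot tell which pair of assumptions was used, and the printed value would still need correcting.

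The second defence is that 50 patients are enrolled, so 14 and 20 are only minimum figures. If 30 of the 50 complete both assessments, power is 81% two-sided even with 0.10 and 0.50. That also stands: the study is not shown to be underpowered. But the 50 must absorb screening failures, refusals and dropouts, no rate is given for any of them, and the justification itself rests on 14 to 20 pairs.

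Third, the 43% risk of a miss depends on three conditions: 0.10 is intended, the test is two-sided 5%, and exactly 20 patients are evaluable. This is correct, and the figure should be read with those conditions attached.

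Whether the listed procedures measure SWS at all is a separate question and does not bear on this arithmetic.

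**Conclusion.** The concern holds. With the printed proportions and the named test, power at 5% is 37% with 14 and 57% with 20 (two-sided), or 49% and 70% (one-sided), against the stated 80% or more and 97%. The 5% level is my assumption, but the missing alpha does not explain the gap, since even one-sided 20% does not reach 97% at 20. The mismatch between inputs and powers is certain. Which side is wrong cannot be settled from the document. If 0.10 and 0.50 are meant, the power is overstated by at least 26 percentage points (97 − 70.3 = 26.7, the smallest of the four gaps at 5%), and 30 pairs two-sided or 25 one-sided are needed for 80%. If a smaller loss proportion is meant, the stated assumption is wrong, and the size of any power error depends on the intended value. This must be corrected, because it is the plan's only power statement.

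**What to change.** In Study Population, item 3:

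1. Confirm the intended success-failure proportion.
2. State alpha and sidedness.
3. Restate the power to match. If 0.10 and 0.50 stand and the test is two-sided 5%, suitable wording would be: *With a success-failure proportion of 0.10 and a failure-success proportion of 0.50, the exact conditional McNemar test at two-sided 5% has power of 37% with 14, 57% with 20 and 81% with 30 evaluable pairs.* If a smaller proportion was meant, correct 1E-1 and recompute at the stated alpha.
4. Give the target as treated patients with both the pre- and post-treatment assessment, separate from the 50 who may be screened, and state the yield assumed between the two.

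The correction itself costs only wording. If 0.10 and 0.50 stand, the stated power becomes less favourable, and whether 50 screened patients can supply 30 pairs depends on screen-failure and dropout rates that the investigators would have to provide.
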